3.2 DISCUSSION OF TRIAL DESIGN, INCLUDING THE CHOICE OF CONTROL GROUP(S)

This is a randomized double-blind, placebo-controlled, parallel-design trial. This design is appropriate for providing proof-of-concept and assessing the safety and efficacy of BI 1358894 compared to placebo in patients with PTSD. It is important to have a placebo control to address potential confounding factors. This is acceptable as patients will remain on their stable background treatment and the duration of the placebo treatment will be limited to 8 weeks.

The design of the trial will provide efficacy and safety of BI 1358895 on PTSD patients to support proof of concept.

Data at Week 8 will provide evidence of efficacy and safety of BI 1358894 compared to placebo. In addition, safety data will also be obtained through the end of observation period (early drug discontinuation date / EOT+28+2 days). Exploratory outcomes from Ecological Momentary Assessments (EcMAs) are intended to assess the disease status in the patients' natural environments. Collectively, this information will help facilitate the design of the Phase III program.

BI 1358894 is regarded as a first in class compound, hence, it was decided to include the review of data by an Independent Data Monitoring Committee (DMC), independent from the sponsor, to review the trial data as a general safety measure. The purpose of the DMC is to ensure that the safety of the patients participating in this trial is maintained by monitoring for possible untoward harmful effects or unexpected frequency of adverse safety events of trial drugs based on emerging data.

The DMC will evaluate and analyse accrued patient data in order to recommend whether the trial or program should continue, be modified or stopped for safety concerns.

The DMC will review pertinent trial data, including SAEs, AEs and laboratory data. DMC meeting frequency and logistics will be specified in a separate DMC Charter.

3.3 SELECTION OF TRIAL POPULATION

A total of approximately 286 patients is planned to be randomized into the trial. It is planned that about 70 trial centers in 10 countries will be participating in this trial to ensure a sufficient number of patients are randomized.

It is expected that approximately 4-10 patients will be randomized at each trial center. If enrolment is delayed, additional sites may be recruited. To avoid differential center influence on trial results, permission to randomize more than 15 patients per site must be obtained from the sponsor. This will only be allowed after a careful review of the enrolment status and the site.

Screening of patients for this trial is competitive, i.e., screening for the trial will stop at all centers when such a number of patients has been screened that it is anticipated that a sufficient number of patients will be randomized to trial treatment. Investigators will be

Page 45 of 148

Proprietary confidential information © 2023 Boehringer Ingelheim International GmbH or one or more of its affiliated companies

notified when the appropriate number of patients has been screened and screening is complete, and will not be allowed to recruit additional patients for this trial. Patients already in screening at this time will be allowed to continue to randomisation, if eligible.

A log of all patients enrolled into the trial (i.e., who have signed informed consent) will be maintained in the Investigator Site File (ISF) irrespective of whether they have been treated with investigational drug or not.

If retrospectively it is found that a patient has been randomized < in error (=did not meet all inclusion criteria or met one or more exclusion criteria), the sponsor or delegate should be contacted immediately. Based on an individual benefit-risk assessment a decision will be made whether continued trial participation is possible or not.

Retesting

Retesting applies in situations when the issue can be resolved within the screening period of 28 days. For example patients that are testing positive on urine drug screen for cannabis or opioids at Visit 1 can be retested once (consider long half-life of cannabis) within the screening period of 28 days, if there is a reasonable explanation and expectation that the patient is not a regular user and will not test positive again on retest or has stable treatment with medically prescribed opioids, both at the discretion of the investigator. In case of retesting, the patient will keep the same patient number. The results of all retests should be available within the 28 days of screening period. Once retests are available and negative for the retested parameter/eligibility confirmed, and in case all other eligibility criteria are met, the patient can be randomized on the planned Visit 2 date.

Rescreening of patients

Rescreening of a patient can be done once, if there is a reasonable explanation and expectation that the patient may have become eligible.

Potential reasons for rescreening could be:

- Active infection with SARS-CoV-2
- Suicidality once the required exclusion period is over
- Clinically significant findings per Investigators judgement
- Restricted medications like CYPs/ alternative or traditional medicine
- Positive urine drug test at screening visit, if longer wash-out period needed

Background therapy must be stable prior to re-screening.

For other potential reasons, please contact the clinical trial leader (CTL).

In case of re-screening, the patient will receive a new patient number. The patient must sign the current, approved version of the informed consent before any study specific procedures are performed.

- If rescreening is done within 12 weeks of screening, all procedures except CTQ, Life Events Checklist and extended Criterion A (as part of the Screening PCL-5) must be repeated. The exceptions above only apply if these assessments are not the reason for rescreening.
- If the rescreening is done more than 12 weeks after the screening, all procedures as shown in the Flow Chart 1 and Flow Chart 2 for Visit 1 must be repeated.

Page 46 of 148

Proprietary confidential information © 2023 Boehringer Ingelheim International GmbH or one or more of its affiliated companies

For all re-screened patients, the screening period will be again 28 days as per protocol. In case all eligibility criteria are met during these repeated screening procedures, the patient can be randomized on the newly planned Visit 2 date.

3.3.1 Main diagnosis for trial entry

Patients with an established diagnosis of Post-Traumatic Stress Disorder confirmed at the time of screening by the Clinician-Administered PTSD Scale for DSM-5 (CAPS-5) will be evaluated for eligibility for the study.

Please refer to section 8.3.1 (Source Documents) for the documentation requirements pertaining to the in- and exclusion criteria.

3.3.2 Inclusion criteria

- 1. Established diagnosis of Post-Traumatic Stress Disorder (PTSD) corresponding to DSM-5 criteria.
- 2. Time since index event according to Life Events Checklist / CAPS-5 Criterion A at least 3 months before screening visit.
- 3. PTSD must be the clinically pre-dominant disorder, as per investigator's judgement. Other comorbid psychiatric disorders are allowed, unless specifically excluded in the exclusion criteria.
- 4. A total severity score of \geq 33 on the PCL-5 at the screening visit.
- 5. Moderate to severe PTSD confirmed by CAPS-5 range \geq 30 confirmed at screening visit.
- 6. Male or female patients, 18 to 65 years of age, both inclusively at the time of informed consent.
- 7. Women who are of child-bearing potential (WOCBP)¹ must be able and willing to use two methods of contraception, as confirmed by the investigator, which include one highly effective method of birth control per ICH M3 (R2) that result in a low failure rate of less than 1%, plus one additional barrier method.
 - A list of contraception methods meeting these criteria and instructions on the duration of their use is provided in section 4.2.2.3.
- 8. Signed and dated written informed consent in accordance with ICH-GCP and local legislation prior to admission to the trial.

A woman is considered of childbearing potential (WOCBP), i.e. fertile, following menarche and until becoming post-menopausal unless permanently sterile.

Permanent sterilisation methods include hysterectomy, bilateral salpingectomy and bilateral oophorectomy.

Tubal occlusion/ligation is NOT a method of permanent sterilisation. A postmenopausal state is defined as no menses for 12 months without an alternative medical cause.

3.3.3 Exclusion criteria

- 1. Corresponding to DSM-5, had ever met diagnostic criteria for schizophrenia, schizoaffective disorder, schizophreniform disorder, bipolar disorder, delusional disorder, brief psychotic disorder or any other psychotic disorder as well as MDD with psychotic features as assessed by the MINI at the time of screening.
- 2. Any psychiatric or non-psychiatric medical condition likely to negatively impact trial participation as per the judgement of the investigator.

Page 47 of 148

Proprietary confidential information © 2023 Boehringer Ingelheim International GmbH or one or more of its affiliated companies

- 3. Acute stress disorder or significant traumatic event within 3 months prior to the screening visit.
- 4. Use of stimulant medications within 3 months prior to the screening visit (Attention Deficit Hyperactivity Disorder (ADHD) diagnosis alone is not exclusionary)
- 5. Severe traumatic brain injury (life-time) or moderate traumatic brain injury within the last 2 years prior to screening visit or 3 months for mild traumatic brain injury, based on the Ohio State University TBI Identification Method Short Form. Or history of traumatic brain injury that would impact ability to complete trial assessments or procedures according to investigator.
- 6. Current treatment with trauma focused therapy (i.e. CPT, PE, EMDR). A psychotherapy in type, intensity and/or frequency other than trauma focused therapy is allowed if stable within the last 8 weeks prior to screening and not anticipated to change during the entire course of the trial. Long-term psychotherapy is permitted as long as patients are not in an exposure phase during the trial.
- 7. Diagnosis of a current moderate or severe alcohol use disorder according to MINI within 3 months prior to screening visit (mild alcohol use disorder (AUD) and patients in early remission = criterion not met for between 3 & 12 months are allowed).
- 8. Diagnosis of a substance use disorder (non-alcohol) according to MINI within 12 months prior to screening visit. Caffeine and nicotine are allowed.
- 9. Positive urine drug screen at the screening visit. Exception: stable opioid-treatment with medically prescribed opioids. Please refer to section 3.3 Retesting for retesting options within the screening period.
- 10. Any suicidal behavior in the past 12 months prior to screening (per investigator judgement including an actual attempt, interrupted attempt, aborted attempt, or preparatory acts or behavior) and during the screening period.
- 11. Any suicidal ideation of type 4 or 5 in the Columbia Suicide Severity Rating Scale (C-SSRS) in the past 3 months prior to screening or at screening or baseline visit (i.e. active suicidal thought with method and intent but without specific plan, or active suicidal thought with method, intent and plan).
- 12. Treatment with benzodiazepines is allowed if stable in dose and frequency of use for at least 2 months prior to randomization visit (please refer to section 4.2.2). Note: PRN- use is not permitted.
- 13. Antipsychotics, antidepressants and other psychiatric medication are allowed if stable in dose and frequency of use for at least 2 months prior to randomization visit (please refer to section 4.2.2)
- 14. Any use of restricted medications within 7 days prior to randomization visit (refer to section 4.2.2).
- 15. Patients who must or wish to continue the intake of restricted medications or any drug considered likely to interfere with the safe conduct of the trial.
- 16. Use of alternative medicine (e.g. Chinese traditional medicine, herbal medication, St. John's wort, etc.) during the entire course of the trial.
- 17. History of seizure disorders, stroke, brain tumor or any other major neurological illness that can impact participation in the trial.
- 18. Any documented active or suspected malignancy or history of malignancy within 5 years prior to screening, except appropriately treated basal cell carcinoma of the skin or in situ carcinoma of uterine cervix.
- 19. Positive result for ongoing Hepatitis B or C infection.

Page 48 of 148

Proprietary confidential information © 2023 Boehringer Ingelheim International GmbH or one or more of its affiliated companies

- 20. Known hypersensitivity to any of the excipients of BI 1358894 or the matching placebos.
- 21. Use of any investigational procedure within 30 days prior to randomization. In case of exposure to an investigational medicinal product, investigator must ensure that it is adequately washed out prior to randomization (at least 5 half-lives of the investigational medicinal product).
- 22. Resting QTcF \geq 450 msec (male) or \geq 460 msec (female) at screening.
- 23. Women who are pregnant, nursing, or who plan to become pregnant while in the trial.
- 24. Patients not expected to comply with the protocol requirements or not expected to complete the trial as scheduled.
- 25. Considered by the investigator, for any other reason, to be an unsuitable candidate for the trial.
- 26. Patients who are currently and during the course of the trial confined to an institution by court or administrative order.
- 27. Patients who are currently involved in any ongoing legal processes related to the index traumatic event (e.g. lawsuit or criminal prosecution).
- 28. Patients currently using Nightware TM Digital Therapeutic tool.
- 29. In-patients are generally excluded, however in-patients who are admitted a voluntary basis in an open-ward (i.e. "residential ward") and are non-suicidal are allowed.
- 30. Major surgery (major according to the investigator's assessment) performed within 4 weeks prior to randomization or planned elective surgery requiring general anesthesia or hospitalization for more than 1 day during the study period, e.g. hip replacement.
- 31. Symptomatic/unstable/uncontrolled or clinically relevant concomitant disease or condition (e.g. renal failure, hepatic dysfunction, cardiovascular disease, etc.) that would jeopardize the patient's safety while participating in the trial or capability to participate in the trial, based on investigator's discretion.

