4.2.2 Restrictions

4.2.2.1 Restrictions regarding concomitant treatment

The following restrictions for comedications are defined for this trial:

- Strong inhibitors of CYP3A4
- Strong inducers of CYP3A4 (please refer to the ISF)

A list of restricted concomitant medications and drugs with potential pharmacokinetic interactions with the trial compound BI 1358894 can be found in the ISF. The list is not

Page 58 of 148

Proprietary confidential information © 2023 Boehringer Ingelheim International GmbH or one or more of its affiliated companies

comprehensive. For example, drugs that are solely indicated for diseases that are excluded in this trial - like cancer drugs - may not be listed.

Use of ECT and Ketamine/S-Ketamine are restricted during the study, and would lead to study discontinuation (refer to section 3.3.4.1).

Patients on statins should be monitored for statin-related toxicity including signs of myopathy, weakness, muscle pain, etc. along with clinical lab results. If statins are concomitantly used during the trial, the highest dose should not be taken together with the investigational compound. If a patient in this trial is on the highest recommended statin dose, investigator should consider changing the statin dose to the next lower dose recommended for the respective statin if appropriate.

Please note:

- Investigators may use their clinical discretion to wash out (at least 3 half-lives of referenced medication) the restricted medications during the screening period. The patient must adhere to the screening visit dose of the allowed background medication for the entire duration of the trial.
- Patients who are on stable treatment with low-dose antipsychotics for treatment of insomnia or similar for at least 2 months prior to randomization should continue without change for the entire trial duration. Antipsychotic treatment for psychiatric symptoms is disallowed.
- Patients who are on stable treatment with ongoing antidepressants for at least 2 months prior to randomization should continue without change for the entire trial duration.
- Patients who are on stable treatment with ongoing benzodiazepine (including Z- drugs) or non-benzodiazepine hypnotics for at least 2 months prior to randomization should continue without change for the entire trial duration.

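### As written, exclusion criterion 9 shuts out the stable benzodiazepine users whom criterion 12 admits, whenever their screening urine test reads positive

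*Protocol*

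**What the plan says.** Criterion 9 in Protocol section 3.3.3, repeated in the synopsis, excludes on this ground: "Positive urine drug screen at the screening visit. Exception: stable opioid-treatment with medically prescribed opioids". It then points to the retesting rules in section 3.3. Table 5.4.3:1 lists the urine panel, and benzodiazepine is on it. The list of drug tests under intercurrent event 3 (Protocol section 7.2.2 and SAP section 6.3) also includes it.

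Criterion 12, in the same exclusion list, is worded as a permission: "Treatment with benzodiazepines is allowed if stable in dose and frequency of use for at least 2 months prior to randomization visit", with as-needed use ruled out. Section 4.2.2.1 covers the same group, "Patients who are on stable treatment with ongoing benzodiazepine (including Z- drugs) or non-benzodiazepine hypnotics for at least 2 months prior to randomization", and directs them to carry on unchanged through the trial. It adds a general rule: "The patient must adhere to the screening visit dose of the allowed background medication for the entire duration of the trial".

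Section 3.3 permits one retest within the 28-day screening period. It gives cannabis and opioids as examples, for a patient who is "not a regular user and will not test positive again on retest or has stable treatment with medically prescribed opioids". The patient may proceed "Once retests are available and negative for the retested parameter/eligibility confirmed", provided all other criteria are met. Rescreening is listed for "Positive urine drug test at screening visit, if longer wash-out period needed".

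**The concern.** Two eligibility rules give opposite answers for the same patient. Someone on a stable, scheduled benzodiazepine satisfies criterion 12. If the screening urine reads positive for that drug, the same person meets criterion 9.

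Section 3.3 plans for about 70 centers in 10 countries, each expected to randomize roughly 4 to 10 patients, and each must settle the question for itself. A center that applies criterion 9 literally turns away patients whom the plan means to study. A center that lets criterion 12 prevail randomizes someone who, in the terms section 3.3 uses for randomization in error, "did not meet all inclusion criteria or met one or more exclusion criteria". That calls for immediate contact with the sponsor and an individual decision on whether the patient continues. The likely results are uneven enrollment of benzodiazepine users across sites and eligibility deviations that need not occur.

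**Working it through.** No power or sample-size figure is involved. The check applies each rule in turn to one patient: stable prescribed benzodiazepine for more than 2 months, not as-needed, with a benzodiazepine-positive urine at Visit 1.

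| Rule | Source | Result for this patient |
|---|---|---|
| Stable benzodiazepine use permitted | 3.3.3, criterion 12 | Permitted |
| Continue unchanged, keep screening-visit dose | 4.2.2.1 | Must stay on the drug |
| Positive screen excludes | 3.3.3, criterion 9 | Criterion met |
| Exception for stable prescribed opioids | 3.3.3, criterion 9 | Does not apply |
| Retest: not a regular user, negative expected | 3.3 | Does not fit: regular user, positive result expected again |
| Retest: stable prescribed opioids | 3.3 | Does not apply |
| Rescreen after a longer wash-out | 3.3 | Conflicts with continuing unchanged |
| No exclusion criterion may be met at allocation | 8.3.1 | Ineligible |

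**Coverage of the exception.** The panel is cannabis, benzodiazepine, barbiturates, opiates, cocaine, amphetamines, methadone and PCP: 8 analytes. The drug classes on it for which the protocol expressly allows stable use are prescribed opioids (section 4.2.2.1) and benzodiazepines (criterion 12 and section 4.2.2.1): 2 classes. Criterion 9 excepts 1 of the 2.

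**Stopping the drug to obtain a negative retest.** The screening period is at most 28 days. With the SAP section 7 conversion, 2 months = 2 × 365.25 / 12 = 60.9 days. Since 28 < 60.9, a patient who stops after Visit 1 cannot show 2 months of stable dosing before randomization in the same screening period. Stopping also breaks the rule on keeping the screening-visit dose.

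**Does permission elsewhere override criterion 9?** Section 4.2.2.1 separately permits stable prescribed opioids, yet criterion 9 still carries an explicit opioid exception. If permission elsewhere were enough, that exception would be unnecessary. Naming one permitted class and leaving out the other invites a site to read the omission as deliberate.

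**The case against.** The strongest reply is that the criteria, read together, have only one sensible meaning. Criterion 12 is a specific permission, section 4.2.2.1 tells these patients to continue, and section 4.2.2.2 links the urine screen to drug abuse rather than to permitted treatment. Letting criterion 9 win would empty criterion 12 wherever the assay detects the drug. On this view a cross-reference is missing, and the intent is not in doubt. That the intent is to admit these patients is accepted. It is not what criterion 9 says, and section 8.3.1 requires evidence that no exclusion criterion is met.

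A second reply is that the retesting text is open. Cannabis and opioids are only examples, the investigator has discretion, and the words after the slash in "Once retests are available and negative for the retested parameter/eligibility confirmed" could be read as an alternative to a negative result. A benzodiazepine retest is indeed possible. But confirming eligibility still means passing criterion 9, and that criterion has no benzodiazepine exception.

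Third, sites can ask the sponsor, and the investigator site file and laboratory manual, which are not available here, may give guidance. It therefore cannot be shown that sites would turn such patients away, and the counts above are of drug classes and days, not of patients. Both points stand and limit what can be said about size. They do not repair the criterion.

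**Conclusion.** The concern holds. A stable benzodiazepine user permitted by criterion 12 who screens benzodiazepine-positive is excluded under criterion 9 as written, and no retesting or rescreening rule reliably clears that patient. This is a stated rule that gives the wrong eligibility result, not merely a missing detail.

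The number of patients affected is unknown. It depends on how many screened patients take benzodiazepines and on whether the assay detects the drug at the prescribed dose, and the documents give neither. The conclusion assumes only that some permitted users will screen positive. The consequences are confined to who is enrolled, consistency across sites, and avoidable deviations. The estimand, the primary analysis and the comparison between arms are not called into question. The change should be made, but the trial's validity does not depend on it.

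**What to change.** Extend the exception in criterion 9 to read:

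> Exception: stable treatment with medically prescribed opioids, or with benzodiazepines permitted under criterion 12, when the positive result matches the prescribed drug.

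Use the same wording in the synopsis and in the section 3.3 retesting text. The matching condition keeps the screen's ability to detect illicit or undisclosed use.

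The cost is one clause in three places, issued by amendment or clarification letter. Sample size, endpoints and analyses do not change.
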